15.3. Efficacy Evaluation

Efficacy analysis will be performed on intent-to-treat population. Adjudicated response will be used for these analyses.

Response

Response, including evaluation of minimal residual disease (MRD), will be assessed by iwCLL guidelines for diagnosis and treatment of CLL (Hallek, 2008). The response rate based on the best response during the treatment period and the relative proportions in each response category will be examined. Exact test procedures for proportions will be used to compare response rate between the treatment arms. Distributions of the responses into the response categories (CR, CRi, nPR, PR, SD, PD) will be provided for each treatment arm. Response rates (CR+CRi+nPR+PR) together with confidence intervals will be provided for each regimen, both for the entire population and for the subgroups defined by the stratification factors.

Responses from subjects after they received other anti-cancer treatments will not be counted, however, these subjects will be included in the denominator.

Duration of Response

Duration of response is defined as the time from the first visit where PR, CRi, or CR was documented to PD. Duration of response will be censored at the last date that the subject was known to be progression-free for: 1) subjects who have not progressed at the time of analysis; 2) subjects who have withdrawn consent or are lost to follow-up prior to documentation of progression.

A two-sided log rank test stratified by the 3 strata used in the randomization at 0.05 significance level will be used to test the duration of response between the two treatment arms.

Time to Response

Time to response is calculated as the time from randomization to the first documented date of PR, CRi or CR based on iwCLL guidelines.

Progression-free Survival (PFS)

Progression-free survival is calculated as the time from randomization to the first documented progression or death due to any cause during or after the treatment period, whichever occurs first. The progression date will be assigned to the earliest time when any progression is observed without prior missing assessments. If withdrawal of consent or loss to follow-up occurs before documented progression or death, then these observations will be censored at the date when the last complete tumor assessments determined a lack of progression.

For subjects who do not develop progressive disease at the time of analysis, if the response from the last visit was 'not evaluable', the most prior visit date with complete evaluation indicating no progressive disease will be used as the censor date.

Event-free Survival (EFS)

Event free survival (EFS) is the interval between the start of treatment to the first sign of disease progression, or treatment for relapse, or death (whichever occurs first)

Time-to-Progression (TTP)

TTP is defined as the time from randomization to the first documented progression. For subjects who do not progress during the study, TTP will be censored at the last adequate response assessment showing evidence of no disease progression. TTP is the same as PFS when there is no death.

Overall Survival (OS)

OS is calculated as the time from randomization to death from any cause. OS will be censored at the last date that the subject was known to be alive for subjects who were alive at the time of analysis and for subjects who have withdrawn consent or were lost to follow-up before death was documented.

The analysis of OS will include survival information for all randomized subjects. Subjects who discontinued from the study and who had possibly received other anti-cancer therapies and then subsequently died will be included in the analysis as death. However, sensitivity analyses may be performed in which these subjects will be censored at the date of the first dose date of the anti-cancer therapy.

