8.1.3. Randomization

Based on consideration of the Bayesian approach the following randomization schema will be followed:

- Initially subjects will be randomized (1:1:1) in a double-blind fashion to the 5 mg, 10 mg, and 15 mg starting dose arms (treatment arm 1, treatment arm 2, and treatment arm 3 respectively).
- After 18 subjects complete one 28 day cycle, an interim analysis will be conducted to review the safety of each starting dose arm(s). Subsequent interim analyses to review the safety and progression rate of each starting dose arm(s) will occur at 13-week intervals. After review of each interim analysis, a treatment arm may be dropped. At any time accrual to a starting dose arm will also be stopped if unacceptable toxicities are observed in that arm. If a treatment arm is dropped then all new subjects will be randomized equally into the remaining arm(s).

Stratification

To minimize potential imbalances within treatment groups due to select patient characteristics that may impact outcomes, study subjects will be stratified by the following criteria at randomization:

 Relapsed versus refractory to their last purine-analog or bendamustine based treatment regimen [relapsed/refractory as defined per the iwCLL guidelines for diagnosis and treatment of CLL (Hallek, 2008)]. If a subject has had prior purineanalog based and bendamustine based regimen, the stratification will be based on subject's status post most recent regimen.

• Age < 65 years of age versus \ge 65 years of age

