### 3. INTRODUCTION

This document describes the statistical analyses and data presentations to be performed for protocol CC-5013-CLL-009 “A Phase 2, Multi-Center, Randomized, Double-Blind, Parallel-Group Study of The Safety and Efficacy of Different Lenalidomide (Revlimid®) Dose Regimens in Subjects with Relapsed or Refractory B-Cell Chronic Lymphocytic Leukemia”.

Subjects were randomized (1:1:1) in a double-blind fashion to the 5 mg, 10 mg, and 15 mg starting dose arms (treatment arm 1, treatment arm 2, and treatment arm 3 respectively).

The randomization procedure was accomplished by a validated interactive voice response system (IVRS). Subjects were stratified at randomization by (i) relapsed vs refractory to their last purine-analog or bendamustine based treatment regimen (if subject has received both, the status post most recent purine-analog or bendamustine regimen was used for stratification) and (ii) age < 65 years of age vs ≥ 65 years of age. The subjects received lenalidomide once daily in a 28 day cycle and will be escalated every 28 days as tolerated in a stepwise manner up to a maximum of 25 mg daily.

Depending on the starting dose, subjects were allocated in a double-blind fashion to three different regimens and will escalate every 28 days, based on individual subject tolerability, as follows:

- Treatment Arm 1: 5 mg →10 mg →15 mg →20 mg →25 mg/daily
- Treatment Arm 2: 10 mg →15 mg →20 mg →25 mg/daily
- Treatment Arm 3: 15 mg →20 mg →25 mg/daily

The primary objective of this study was to evaluate the safety of different lenalidomide dose regimens in subjects with relapsed or refractory B-cell chronic lymphocytic leukemia (CLL). The secondary objective was to evaluate the efficacy of different lenalidomide dose regimens in subjects with relapsed or refractory B-cell CLL.

This study was conducted using a randomized Bayesian schedule-administration design that jointly models toxicity/disease progression outcomes using an extension method. The object of interest was to determine if a particular treatment administration schedule is superior to other competing schedules. No treatment arm was stopped during the conduct of the study.

In total 104 subjects were enrolled into the study.

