### 6.2. Randomization and Stratification

Stratification and randomization will be performed by IVRS, an Interactive Voice Response System, to ensure a 1:1:1 central randomization. Subjects will be stratified at randomization by:

- Relapsed versus refractory to their last purine-analog or bendamustine based treatment regimen [relapsed/refractory as defined per the iwCLL guidelines for diagnosis and treatment of CLL (Hallek, 2008). If a subject has had prior purine-analog based and bendamustine based regimen, the stratification will be based on the subject's status post most recent regimen.
- Age < 65 years of age versus  $\geq$  65 years of age

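### Protocol 15.3 plans a two-arm, three-stratum log-rank test of duration of response in a three-arm, four-stratum trial; SAP 11 omits it and the exact test of response rate without saying so, and nPR is missing from three start definitions

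*Protocol*

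**What the plan says.** **Duration of response.** Protocol 15.3 prescribes a two-sided "log rank test stratified by the 3 strata used in the randomization at 0.05 significance level", to be used "to test the duration of response between the two treatment arms". The synopsis (Statistical Analysis, Efficacy Analysis) says only that response, duration of response and the other time-to-event endpoints will be summarized, with Kaplan-Meier where there is censoring. SAP section 11 gives Kaplan-Meier estimates by arm and an optional median with confidence interval. It names no test.

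**Response rate.** Protocol 15.3 states: "Exact test procedures for proportions will be used to compare response rate between the treatment arms". The corresponding SAP paragraph keeps the response categories, the rates and the confidence intervals, but not that sentence.

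**Design.** Protocol 8.1.3 says "Initially subjects will be randomized (1:1:1) in a double-blind fashion" to the 5, 10 and 15 mg starting doses, and SAP 6.2 uses the voice-response system "to ensure a 1:1:1 central randomization". Stratification is by relapsed or refractory status and by age below 65 or not. SAP section 3 adds: "No treatment arm was stopped during the conduct of the study".

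**nPR.** Both documents count nPR in the response rate. Both start duration of response at the first visit with a documented PR, CRi or CR. The protocol dates time to response from the "first documented date of PR, CRi or CR based on iwCLL guidelines"; the SAP's version adds nPR to that list.

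**Relation between the documents.** SAP section 3 says the SAP specifies the analysis pre-planned in the protocol. Its table of contents has no section on changes from the protocol.

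**The concern.** A test that names two arms in a three-arm trial has no defined contrast. Three pairwise comparisons and one global comparison all fit the sentence, and no multiplicity rule for this endpoint is visible. The strata count is wrong too, though the intended strata can be identified.

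The two documents then disagree on whether duration of response and response rate are tested between arms at all. If the protocol governs, two planned tests are missing from the SAP. If the SAP governs, the protocol still promises tests that nobody intends to run, and no text records the decision.

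Finally, a subject whose documented response is nPR is a responder in the rate, but is given no start date by the literal definition of duration of response, or by the protocol's definition of time to response. As written, time to response is defined differently in the two documents.

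**Working it through.** **1. Arms and strata**

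- Arms: 105 planned subjects at 35 per arm (Protocol 15.10; SAP 6.1) gives 105 / 35 = 3. The log-rank sentence says two. A dropped arm does not explain this, because SAP section 3 reports that none was stopped.
- Strata: two factors with two levels each (Protocol 8.1.3 and 10.2.1; SAP 6.2) give 2 × 2 = 4 cells. Counting factors instead gives 2. Neither count gives the stated 3.

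**2. What the undefined contrast leaves open**

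- Pairwise contrasts among three arms: 3 (5 v 10, 5 v 15, 10 v 15 mg). The alternative is one global test on 3 − 1 = 2 degrees of freedom.
- If all three pairs were each tested at 0.05, the chance of at least one false positive would be 1 − 0.95³ = 0.143 for independent tests. With equal arms and the correlation between pairs taken into account, it is 0.122 (large-sample studentized range for three groups, at 1.96 × √2). A single global test would hold it at 0.05.
- No power, effect size or event count is visible for this test in Protocol 15.10, so there is no planned figure to reproduce.

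**3. How thin a stratified test would be (illustration)**

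SAP section 3 says "In total 104 subjects were enrolled into the study". Assume response rates from the background studies in Protocol 5.3.2, equal arms (104 / 3 = 34.7) and equal strata.

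| Background study | Rate | Responders of 104 | Per arm | Per arm per stratum |
|---|---|---|---|---|
| Amended CC-5013-CLL-001 study (5.3.2.3) | 6/52 | 12.0 | 4.0 | 1.0 |
| 10 mg start with titration (5.3.2.1) | 14/44 | 33.1 | 11.0 | 2.8 |
| 25 mg, 21 of 28 days (5.3.2.1) | 26/45 | 60.1 | 20.0 | 5.0 |

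These studies used other regimens, and the last added rituximab at progression. The table shows only an order of magnitude: a handful of responders per arm within each stratum.

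**4. The two documents side by side**

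| Item | Protocol 15.3 | Protocol synopsis | SAP 11 |
|---|---|---|---|
| Duration of response | Kaplan-Meier not mentioned; log-rank, two arms, 3 strata | Summary, Kaplan-Meier | Kaplan-Meier, no test |
| Response rate | Exact test between arms, rates with CIs | Summary | Rates with CIs, no test |
| nPR counts as response | Yes | – | Yes |
| nPR starts duration of response | No | – | No |
| nPR starts time to response | No | – | Yes |

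No redaction is marked in SAP section 11, so the missing tests are not a redaction effect. The SAP does carry over the protocol's optional exact test for adverse events (Protocol 15.8; SAP 12.1), so it names that retained test.

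**The case against.** The best defence is that the intention is fairly clear. The synopsis and SAP section 11 agree on a descriptive analysis, and the log-rank sentence is the outlier. Protocol 15.5 also refers to both regimens, where SAP section 8 refers to all arms, which suggests text carried over from a two-arm template. This has force. It makes the descriptive option the natural repair and weakens any claim that the reader is left without guidance. It does not cure Protocol 15.3, which still contains an operative testing rule, and it does not make the SAP's omissions declared.

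It can also be said that comparison between arms is not absent. Protocol 15.4 and SAP 13.3 plan classical and Bayesian regressions with treatment as a covariate, and SAP 13.4 plans comparisons within the stratification subgroups. Neither section names an endpoint, so neither replaces the two tests.

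On nPR, a reader may treat it as a kind of PR, since the SAP admits subjects with PR or better to the duration curve. But the SAP lists PR and nPR as separate items under time to response, so the definition needs to say what it means.

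Three stronger readings are tempting and are not supported:

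- *That an nPR found on marrow moves the start date by 8 to 12 weeks.* Protocol 8.1.8 and 12.2 schedule response marrow only for subjects who have already reached CR or CRi. Such a subject already has a qualifying visit, and the first-visit rule selects that earlier date.
- *That a countable number of responders drops out of the duration analysis.* Such a count would combine response rates from studies that report no nPR with nPR shares from other studies, one of them in untreated patients. The documents give no usable estimate for this trial.
- *That the contrast could be picked with unblinded results in view.* SAP section 11 contains no test whose contrast could be picked, adjudication is blinded (Protocol 8.1.8), and the SAP is to be final before database lock for the PFS analysis.

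**Conclusion.** The concern holds as an error in a stated analysis rule, together with an undeclared difference between the documents. The log-rank test names two arms against three and three strata against four, and cannot be run as written. Two between-arm tests in Protocol 15.3, log-rank for duration of response and exact for response rate, have no counterpart in SAP section 11. nPR is missing from three definitions: duration of response in each document, and time to response in the protocol.

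The counts of arms, strata and omitted tests come directly from the documents. The responder counts rest on assumed rates from other regimens and bear only on which repair is more sensible. The effect is confined to secondary endpoints of a phase 2 trial whose primary endpoint is safety; no visible power statement or stopping decision depends on these tests. It should be corrected, but it does not threaten the trial's main conclusions.

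**What to change.** - **Duration of response.** In Protocol 15.3, either delete the log-rank sentence and state that the analysis is descriptive (Kaplan-Meier by arm), as in the synopsis and SAP section 11, or replace it with one three-arm log-rank test on 2 degrees of freedom, stratified by the two randomization factors, and add the same test to SAP section 11. The first option needs less change and suits the small strata illustrated above.
- **Response rate.** Either delete the exact test from Protocol 15.3, or name one three-arm exact test in both documents.
- **nPR.** Add it to the start of duration of response in Protocol 15.3 and SAP section 11, and to time to response in Protocol 15.3.
- **Record.** List each item as a declared change.

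The cost is wording in two documents and minor reprogramming of the derived start dates. No new data are needed.

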15.2. Study Population Definitions

15.2.1. Intent-to-Treat Population

The efficacy analysis will be performed on the ITT population, which will include all subjects randomized.

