15.10. Sample Size and Power Considerations

The sample size will be approximately 105 subjects, 35 per arm, barring early stopping. The original accrual rate was assumed to increase with time such that approximately 9-12 subjects will accrue in the first 3 months and a total of 41 to 55 subjects will accrue by 6 months with the remainder accruing by 60 weeks. Therefore, in addition to monitoring toxicity and progression, the accrual rate will be monitored.

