### Duration of Response

Duration of response is defined as the time from the first visit where PR, CRi, or CR was documented to PD. Duration of response will be censored at the last date that the subject was known to be progression-free for: 1) subjects who have not progressed at the time of analysis; 2) subjects who have withdrawn consent or are lost to follow-up prior to documentation of progression.

For subjects who achieved at least a PR, Kaplan-Meier product limit methods will be used to estimate the survival functions for each treatment arm. Median duration of response along with two-sided 95% confidence intervals (CIs) may be estimated.

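### The protocol's log-rank test of duration of response compares responders only, so it is not a randomized comparison and can point against an arm that merely adds short responses

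*Protocol*

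**What the plan says.** Protocol section 15.3 defines the endpoint from the response date: "Duration of response is defined as the time from the first visit where PR, CRi, or CR was documented to PD". It then names the method: "A two-sided log rank test stratified by the 3 strata used in the randomization at 0.05 significance level". The purpose given for this method is a comparison of arms, since the sentence ends by saying that it "will be used to test the duration of response between the two treatment arms". The same section opens with "Efficacy analysis will be performed on intent-to-treat population", and section 15.2.1 defines that population as all subjects randomized. Neither section gives a duration value, such as zero, for a subject who never responds.

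SAP section 11 handles the endpoint differently. It has no between-arm test and restricts the analysis openly: "For subjects who achieved at least a PR, Kaplan-Meier product limit methods will be used to estimate the survival functions for each treatment arm". On medians it is non-committal: "Median duration of response along with two-sided 95% confidence intervals (CIs) may be estimated". It does not say that the curves by arm are descriptive.

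The planned size is three arms of 35 (Protocol section 15.10). Neither document gives a power, effect size or event count for duration of response.

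**The concern.** Responder status arises after randomization, and the trial exists because starting dose may affect efficacy. Protocol section 5.3.3 says that starting above 2.5 mg daily may provide superior efficacy, and section 15.1 says the aim is to learn whether one schedule is superior to the others. If arms differ in who responds, their responders differ in prognosis, and a log-rank test between them mixes the effect of dose with that difference. Stratifying on baseline factors does not undo selection on an outcome.

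The awkward case is an arm that turns some non-responders into brief responders. Nobody in that arm is worse off and some are better off, yet its responder-only curve drops and the test leans against it. A reader of a 0.05-level result would take it as evidence that the schedule gives less durable benefit.

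**Working it through.** **The plan's own figure.** 3 × 35 = 105, which agrees with section 15.10. There is no power statement for this endpoint to reproduce.

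**Arithmetic without sampling (assumed counts).** Arm A has 11 of 35 responding for 12 months each. Arm B has the same 11 plus 7 responding for 3 months each.
- Mean among responders: A 12.0; B (11×12 + 7×3)/18 = 153/18 = 8.5 months.
- Mean per randomized subject, non-responders at zero: A 132/35 = 3.8; B 153/35 = 4.4 months.

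The ordering reverses with the denominator.

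**Main example (assumed).** 35 per arm, exponential durations. Arm A has 30% responders with median 12 months. Arm C has the same 30% plus 20 points with median 4 months.
- Responder median in C: long and short responders are in the ratio 0.6 to 0.4, so solve 0.6·2^(−t/12) + 0.4·2^(−t/4) = 0.5. This gives t = 7.5 months, against 12 in A.
- Mean time in response per randomized subject is the sum of rate × median/ln 2. A: 0.30 × 12/0.693 = 5.2. C: 5.19 + 0.20 × 4/0.693 = 5.19 + 1.15 = 6.3 months. Capped at 60 months the values are 5.0 and 6.2.
- Simulated log-rank on responders (two arms, unstratified, censored at 60 months):

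| | Points against C | Significant against C | Significant for C |
|---|---|---|---|
| C adds short responses | about 77% | about 12% | about 0.5% |
| Identical durations | about 50% | about 3-4% | about 3-4% |

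**Sensitivity, with inputs taken from Protocol section 5.3.2 where possible.** Base response rates of 12%, 32% and 57.7% come from the earlier studies cited there. Long responses have an assumed median of 7.7 months, from a responder median PFS of 12 months less a median time to response of 4.3 months. Subtracting medians is only an approximation, so 12 months was also tried. Short responses have an assumed median of 3 or 4 months, including the 8-week minimum for a confirmed response. At a 32% base and a short median of 3 months:

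| Extra short responses | Responder median, A vs B (months) | Mean time in response per randomized subject, A vs B (months) | B significantly worse |
|---|---|---|---|
| +10 points | 7.7 vs 5.8 | 3.3 vs 3.6 | 8% |
| +20 points | 7.7 vs 4.7 | 3.3 vs 4.0 | 15% |
| +30 points | 7.7 vs 4.2 | 3.3 vs 4.3 | 23% |

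Over all scenarios with extra responses, B was significantly worse in about 5% to 28% of trials, against 3-4% with identical durations. In every one of them B had the higher mean time in response over all randomized subjects.

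**The case against.** **The SAP has already dropped the test.** It also states the responder population openly. This stands, and it narrows the defect to a protocol sentence that still prescribes the test, plus responder-only curves by arm that carry no descriptive label.

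**The sentence cannot be run as written.** It refers to two arms in a three-arm trial, and to three strata where two binary factors give four cells. This is true, but correcting those words would leave the selection problem in place. The simulation is therefore an unstratified two-arm illustration, not the specified test.

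**The size depends on assumptions.** No figure in the documents supports a 20-point gain made up entirely of short responses. This stands. Significance against the better arm is uncommon because responders are few; the excess in the main example is about 8 to 9 points.

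Three stronger readings are tempting, and the documents do not support them.
- A reader might infer that section 15.2.1 is contradicted. That section says "The efficacy analysis will be performed on the ITT population, which will include all subjects randomized", which names a population. An endpoint defined only in responders is a subset of that population; the fault is lost comparability.
- A reader might infer that nothing is reported on all randomized subjects. SAP section 11 gives response rate, PFS, TTP and OS by arm on the intent-to-treat population. In the main example the 30% versus 50% response rates would be displayed too. Only an all-randomized measure of time in response is missing.
- A reader might infer that the trial could discard the better schedule. The visible interim rules (Protocol synopsis, sections 8.1.2 and 15.9) use toxicity and progression, and SAP section 3 reports that no arm was stopped.

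**Conclusion.** The concern holds for the test in Protocol section 15.3. As defined, duration of response can be compared only among responders, so the log-rank test is not a randomized comparison. It can favour the wrong arm whenever one arm's extra responses are shorter than the rest. That direction follows from the construction. The size rests on assumed durations and response gains: in the main example, a responder median of 12 versus 7.5 months against 5.2 versus 6.3 months in response per randomized subject, with about 12% of trials significant against the better arm instead of about 3-4%.

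The weight is limited. The endpoint is secondary, the primary endpoint is safety, and the SAP no longer lists the test. The change should still be made, because the two documents disagree and the SAP's curves by arm invite the same misreading.

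**What to change.** 1. Delete the between-arm test of duration of response from Protocol section 15.3, so that it agrees with SAP section 11.
2. State in both documents that responder-only duration of response by arm is descriptive and is not a comparison of arms.
3. Rest any between-arm claim about durability on all randomized subjects. Use the planned PFS and, as a supportive analysis, mean time in response up to a fixed horizon from randomization. Count non-responders as zero and let progression or death end a response.
4. Handle censoring before the horizon by subtracting two Kaplan-Meier curves: time to progression or death, minus time to the first of response, progression or death. The gap at each time estimates the probability of being in response, and the area between the curves up to the horizon is the mean time in response. A subject who never responds has the same time in both curves and so contributes nothing.

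The cost is a wording change in each document, one extra table and one figure from dates already collected for the planned endpoints, and a horizon that must be fixed before the analysis.

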In August 2012, a decision was made to deviate from the randomization procedure and enroll the last subject into the 10mg cohort in order to have at least 6 valid (with sufficient PK samples) subjects in each starting dose level into the PK sub-study of the trial.

Per the Monitoring Committee (DMC) meeting on 10 May 2012, a unanimous decision was made to unblind the study in December 2012.

This statistical analysis plan (SAP) provides a comprehensive and detailed description of the rationale and statistical techniques to be used to achieve the objectives of the study. It specifies the pre-planned analysis in the study protocol, and provides additional details concerning the planned and exploratory analyses that will be conducted for all the data collected during the study and in the follow-up phase. The SAP will be finalized and approved prior to the clinical database lock for the planned analysis on progression-free survival (PFS), and updated for overall survival (OS) analyses as appropriate.

All statistical analyses will be conducted using SAS® Version 9.1 or higher.

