### **Overall Survival (OS)**

Overall survival is calculated as the time from randomization to death from any cause. OS will be censored at the last date that the subject was known to be alive for subjects who were alive at the time of analysis and for subjects who have withdrawn consent or lost to follow-up before death was documented.

The analysis of OS will include survival information for all randomized subjects. Subjects who discontinued from the treatment phase of the study and who had possibly received other anti-cancer therapies and then subsequently died will be included in the analysis as death.

Kaplan-Meier product limit methods will be used to estimate the survival functions for each treatment arm and overall. Median OS along with two-sided 95% confidence intervals (CI) will be estimated.

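### The optional OS sensitivity analysis in protocol 15.3, as worded, censors at new therapy only the subjects who later died, so censoring depends on a future event

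*Protocol*

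**What the plan says.** Protocol 15.3 (Efficacy Evaluation, Overall Survival) defines the endpoint: "OS is calculated as the time from randomization to death from any cause". Three rules follow.

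- **Subjects alive:** "OS will be censored at the last date that the subject was known to be alive for subjects who were alive at the time" (the time meant is that of the analysis). No exception is made for a living subject who has started another therapy.
- **Deaths after other therapy, main analysis:** those who discontinued and "had possibly received other anti-cancer therapies and then subsequently died will be included in the analysis as death".
- **Deaths after other therapy, sensitivity analysis:** "sensitivity analyses may be performed in which these subjects will be censored at the date of the first dose date" (the dose meant is the first one of the other therapy).

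SAP Section 11 (Overall Survival) repeats the main rule with a small edit, now referring to subjects who "discontinued from the treatment phase of the study and who had possibly received other anti-cancer therapies". It leaves out the sensitivity sentence. For OS it plans only estimation: "Kaplan-Meier product limit methods will be used to estimate the survival functions for each treatment arm and overall", with medians and 95% confidence intervals. SAP Section 3 says the plan will be "updated for overall survival (OS) analyses as appropriate".

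**The concern.** In the sensitivity sentence, the words for the censored group point back to the sentence before, and that group is defined by having died. Two subjects who start the same new therapy on the same day are then treated differently according to what happens later. The one who dies is censored on that day. The one who lives is followed as event-free to last contact. Valid censoring at a time point may use only what is known by then; this rule uses the later outcome.

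A sensitivity analysis of this kind is usually read as a check that later therapy does not drive the OS result. Under this wording the curve can move because arms differ in how often subjects change therapy, even when mortality is the same. A reader comparing the three starting-dose arms could take such a difference for a survival signal.

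**Working it through.** **1. Mechanism.** Take the subjects in one arm who start other therapy. Let *d* be those who later die, with post-switch follow-up P_d, and let P_a be the post-switch follow-up of those still alive.

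- Main analysis: post-switch death rate = d / (P_d + P_a).
- Rule as worded: the *d* deaths and P_d are removed and P_a is kept, so the rate is 0 / P_a = 0.
- Every switcher censored at the switch: no deaths and no time after the switch, so this period does not enter.

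Under the rule as worded, switchers add event-free time and never an event.

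**2. The plan's own figures.** None exist for this analysis: no alpha, effect size or event count is given for OS. The sample size of about 105 agrees with 3 × 35 = 105. The size of the bias therefore has to be simulated.

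**3. Inputs.**
- 35 per arm and accrual over 60 weeks (protocol 15.10). 60 weeks is 60 × 7/30.4 = 13.8 months by the SAP 6.5.3 conversion.
- Cut-off five years after the last randomization (protocol 14.1, taking the full five years), so follow-up is 60 to 73.8 months.
- Median OS 16 and 32 months. These are assumptions, taken from the alemtuzumab study in protocol 5.1.
- Exponential death times, and exponential switching independent of death with median 24, 12 or 6 months. These are assumptions; the documents give no switching rate.

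Closed-form checks: the share switching before death is median OS / (median OS + median time to switch), for example 16/(16 + 24) = 0.40. True 60-month OS is 2^(−60/16) = 0.074 or 2^(−60/32) = 0.273.

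**4. Kaplan-Meier results, 200,000 subjects per row, mortality the same within each median-OS block.**

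| Median OS (months) | Median time to switch (months) | Switch | Die (main) | Deaths counted, as worded | 60-month OS, main | As worded | All switchers censored |
|---|---|---|---|---|---|---|---|
| 16 | 24 | 40% | 94% | 59% | 0.074 | 0.159 | 0.074 |
| 16 | 12 | 57% | 94% | 43% | 0.075 | 0.261 | 0.076 |
| 16 | 6 | 73% | 94% | 27% | 0.074 | 0.428 | 0.070 |
| 32 | 24 | 55% | 76% | 41% | 0.273 | 0.453 | 0.272 |
| 32 | 12 | 72% | 76% | 27% | 0.272 | 0.589 | 0.277 |
| 32 | 6 | 84% | 76% | 16% | 0.271 | 0.735 | 0.280 |

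**5. A milder setting.** Assume median OS 36 months, follow-up 60 to 96 months, and 30%, 50% or 70% of subjects liable to switch with median 8 months, so that 25%, 41% or 57% switch before death. True 36-month OS of 0.50 reads 0.53, 0.56 and 0.60 as worded. Censoring all switchers gives 0.50 each time.

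**6. Two arms, equal mortality, 35 per arm.** Two-sided 5% log-rank test, 4,000 trials, Monte Carlo standard error about √(0.05 × 0.95/4000) = 0.3 percentage points. The test only measures how far apart the arms can look; the plan has no OS test. Rejection under the rule as worded:

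| Median time to switch, arm vs arm (months) | Median OS 16 | Median OS 32 |
|---|---|---|
| 12 vs 12 | 5.2% | 5.2% |
| 24 vs 12 | 6.9% | 10.3% |
| 12 vs 6 | 6.7% | 9.5% |
| 24 vs 6 | 8.8% | 23.7% |

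The main analysis rejects 5.2% to 5.8% throughout, and censoring all switchers 4.3% to 5.6%. In the setting of step 5, with 25% versus 57% switching, the rule as worded rejects about 13%, against about 5% for either alternative.

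**7. Does the estimate still follow mortality?** With equal switching (median 12 months) and median OS 12, 16, 24 and 32 months, 24-month OS as worded is 0.274, 0.398, 0.572 and 0.678, against 0.251, 0.354, 0.501 and 0.595 in the main analysis. It does.

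**8. Is the shift always upward?** No. With median OS 12 months, median time to switch 12 months and the death hazard halved after switching (all assumed), median OS is 14.6 months in the main analysis and 13.3 months as worded.

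**The case against.** The strongest reply is that this is loose drafting of an analysis nobody has scheduled. The protocol only permits it. The SAP rewrites the OS paragraph and drops the sentence, and the only sensitivity analysis in SAP Section 11 uses the investigator's assessment. The SAP's remark about updating for OS is conditional and does not show that this analysis will return. OS is one of seven secondary endpoints in a trial whose primary endpoint is safety.

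The sentence also cannot be applied quite literally. Its group includes subjects who only possibly received other therapy, and those who received none have no first-dose date. A programmer would have to interpret it, and might choose the conventional rule of censoring every switcher. The authors may have meant that.

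The sizes depend on assumed survival and switching rates. Nothing in the documents says that the arms will switch at very different rates, and all three regimens escalate toward the same maximum.

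All of this stands and limits the weight of the point. It does not make the rule sound. The sentence is still in the current protocol, subsequent CLL therapies are collected (protocol 14.1), and someone following the text would censor on a later death.

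**Conclusion.** The rule is wrong as worded, and the correction is minor. It selects subjects for censoring by a future event. In the settings examined without a post-switch benefit, it raises OS by an amount that grows with switching, and it can make arms of equal mortality look different when their switching differs. The shift ranges from 0.03 in 36-month OS (25% switching, median OS 36 months) to more than 0.4 in 60-month OS (84% switching, median OS 32 months). False-positive rates under unequal switching run from about 7% to 24%. All of these figures rest on the assumed rates.

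Four stronger readings are tempting and are not supported:

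- A reader might infer that the result reflects switching instead of mortality. Deaths before new therapy still count and the estimate follows mortality (step 7), so it depends on both.
- A reader might infer that OS always lengthens. Step 8 is a counter-example.
- A reader might infer that the worse-tolerated regimen gains. The documents do not link toxicity stops to the rate of starting new CLL therapy.
- A reader might infer that the reported OS result is at risk. The main analysis counts every death and is untouched, no OS test is planned, and the SAP does not carry the sensitivity analysis.

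**What to change.** Choose one of two changes to protocol 15.3.

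1. Delete the sensitivity sentence, which brings the protocol into line with SAP Section 11.
2. Replace it, and add the same text to the SAP's OS section: *As a supportive sensitivity analysis, every subject who starts another anti-cancer therapy will be censored at the start of that therapy, whether or not the subject later dies; the number censored will be shown by arm.*

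Under the second option, state that the analysis assumes switching is unrelated to prognosis, which is doubtful after progression. For example, in the setting of step 5 with 57% switching and the death hazard doubled after the switch, 36-month OS is 0.37 in the main analysis, 0.54 under the present wording and 0.50 with all switchers censored. The replacement therefore answers a different question from the main analysis and should be read as supportive only.

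The cost is one sentence and no new data, since subsequent CLL therapies are already collected. The downside of the second option is fewer person-months and fewer events. The main OS analysis does not change.
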